9.1.1 Suspected adverse reaction

A suspected adverse reaction means any adverse event for which there is a reasonable possibility that the drug caused the adverse event. Reasonable possibility means there is evidence to suggest a causal

relationship between the drug and the adverse event. A suspected adverse reaction implies a lesser degree of certainty about causality than adverse reaction.

9.1.2 Adverse reaction

An adverse reaction means any adverse event caused by a drug. Adverse reactions are a subset of all suspected adverse reactions for which there is reason to conclude that the drug caused the event.

9.2 Serious Adverse Event

A serious adverse event (SAE) or suspected adverse reaction is any untoward medical occurrence that, in the view of either the investigator or sponsor, it:

- Results in death;
- Is considered to be life-threatening;
- Requires inpatient hospitalisation or prolongation of existing hospitalization;
- Results in persistent or significant disability, incapacity or substantial disruption of the ability to conduct normal life functions;
- Results in a congenital anomaly or birth defect;
- Is an important medical event that may not result in death, be life-threatening, or require hospitalisation but may be considered serious when, based upon appropriate medical judgment, they may jeopardise the patient or subject and may require medical or surgical intervention to prevent one of the outcomes listed in this definition.

9.2.1 Life threatening

Life threatening refers to an adverse event or suspected adverse reaction in which, in the view of the investigator or sponsor, the subject was at immediate risk of death at the time of the event; it does not include an event that might have caused death if it were more severe.

Any event requiring inpatient hospitalisation (or prolongation of hospitalization) that occurs during the course of a subject's participation in a clinical study must be reported as a serious adverse event, except hospitalizations for the following:

- Social reasons in absence of an adverse event;
- Surgery or procedure planned before entry into the study (must be documented in the CRF)

9.2.2 Unexpected

An adverse event or suspected adverse reaction is considered unexpected if it is not listed in the Investigator's Brochure or is not listed at the specificity or severity that has been observed; or, though they are mentioned as occurring with a class of drugs or as anticipated from the pharmacological properties of the drug, they are not specifically mentioned as occurring with the particular drug under investigation.

9.3 Suspected unexpected serious adverse reaction (SUSAR)

A suspected unexpected serious adverse reaction (SUSAR) is a suspected adverse reaction that is both serious and unexpected.

9.4 Relationship

Relationship to the investigational product:

The relationship of the investigational product to an adverse event must be determined using the following classification:

None:	No relationship with investigational product.
Possible:	Reasonable possibility that the event was caused by the investigational product.
Related:	The event was certainly or probably caused by the investigational product.

Relationship to the surgical procedure:

None:	No relationship to the surgical procedure.
Possible:	Reasonable possibility that the event was caused by the surgical procedure.
Related:	The event was certainly or probably caused by the surgical procedure.

9.5 Severity

The following definitions should be used to determine the severity rating of all AEs:

Mild:	Awareness of signs or symptoms, but these are easily tolerated and are transient and mildly irritating only. There is no loss of time from normal activities and symptoms do not require medication or a medical evaluation.
Moderate:	Discomfort enough to cause interference with usual activities or require therapeutic intervention, such as concomitant medication.
Severe:	Incapacity with inability to work or do usual activities.

9.6 Collection of Adverse Events

AEs will be recorded as they are reported, whether spontaneously volunteered or in response to questioning about well-being. AEs will be collected from the start of randomisation at the baseline visit, throughout the hospital admission, and until completion of the 30-day follow-up visit.

Details of all AEs occurring during the study must be recorded on the AE form with the following information:

- Description of the event
- Dates of onset and resolution
- Severity
- Action taken
- Outcome
- Relationship to investigational product
- Whether the AE is serious or not

All AEs will be documented in the subject's source documents (e.g. medical records) and eCRF. All AEs will be followed until completion of the 30-day follow-up visit or until a stable resolution, whichever is sooner.

Expectedness of an SAE will be defined based on whether the specificity or severity of which is not consistent with the current Investigator's Brochure.

Other: The investigator may also need to consider whether an event is attributable to the investigational product, based on insufficiencies or inadequacies in the instructions or as a result of user error. The investigator must contact the Sponsor should this occur.

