At least 40 qualified paediatric subjects with an appropriate mild or moderate bleeding Target Bleeding Site (TBS) will be randomised in a 1:1 allocation ratio to either EVARREST or SURGICEL (control). Absolute time to haemostasis will be assessed as well as haemostasis at 4 and 10 minutes from randomisation.

Enrolment will be staggered by age (as required by the European Medicines Agency (EMA) Paediatric Committee). The first 36 subjects enrolled will be aged ≥ 1 years to <18 years of age. Enrolment of a subsequent group will include 4 subjects from 1 month (≥ 28 days from birth) to <1 year of age will follow. Ongoing safety assessment will ensure adequate safety monitoring occur during the staged enrolment.

Subjects will be followed post-operatively through hospital discharge and at 30 days (+/-14 days) post-surgery.

TBS DEFINITION: The Target Bleeding Site (TBS) will be defined as the first accessible mild or moderate bleeding site identified in the hepatic parenchyma or soft tissue, where conventional methods of controlling bleeding are ineffective or impractical, and is amenable to manual compression. The TBS must be a site where occlusion of the injured tissue surface blood vessels is required to achieve haemostasis.

The TBS must be an area that can have firm pressure applied and maintained continuously until 4 minutes after randomisation, and to which EVARREST can be applied with a margin of 1-2cm. (Refer to Investigator's Brochure).

EVARREST should not be used on large defects in arteries or veins where the injured vascular wall requires repair with maintenance of vessel patency and which would result in persistent exposure of the EVARREST to blood flow and pressure during healing and absorption of the product. EVARREST should not be used in place of sutures or other forms of mechanical ligation for the primary treatment of major arterial bleeding.

BLEEDING

SEVERITY:

Mild Bleeding: a TBS with a small area of capillary, arteriole or venule oozing

Moderate Bleeding: a TBS with a larger area of capillary, arteriole, or venule oozing that presents a significant challenge because of the larger area involved, increasing the volume of blood loss,

Or

A TBS with bleeding that is more pronounced than oozing, that could also come from a small artery or vein, but is not massive.

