EVARREST Sealant Matrix/EVARREST Fibrin Sealant Patch (EVARREST) is a topical absorbable haemostat and will be evaluated in this study to measure its safety and effectiveness in controlling mild/moderate bleeding from hepatic parenchyma or soft tissue as required by the Paediatric Investigational Plan.

The Product

EVARREST is a sterile bio-absorbable combination product consisting of two constituent parts—a flexible backing and a coating of two biological components (Human Fibrinogen and Human Thrombin). The product has been developed for the management and rapid control of bleeding, including active, challenging bleeding.

The primary mechanism of action of EVARREST follows the principles of normal physiological fibrin clot formation. Upon contact with a bleeding wound surface, the biological components (Human Fibrinogen and Human Thrombin) on the matrix hydrate and the subsequent fibrinogen-thrombin reaction initiates the last step of blood clot formation in a normal and well-understood biochemical reaction. Haemostasis occurs when fibrinogen is converted into fibrin monomers, which spontaneously polymerize to a fibrin clot, forming a sealing layer that adheres to the tissue surface and integrates into the matrix. The matrix component provides physical support and a large surface area for the biological components, imparts inherent mechanical integrity to the product and supports clot formation. Natural healing occurs as the

product is absorbed by the body, which is expected to occur within approximately 8 weeks, as demonstrated in rodent and swine animal models.

The patch component of EVARREST consists of an oxidized regenerated cellulose (ORC) layer underlying a layer of polyglactin 910 (PG910) non-woven fibers. The PG910 layer contains the embedded biological components. The patch component provides a large surface area for the biological components and imparts inherent mechanical integrity to the product. The flexibility of EVARREST accommodates the physiological movements of tissues and organs.

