7.1.4 Post-Surgery until Hospital Discharge

Prior to discharge, the following blood samples must be drawn and data will be recorded:

- Blood samples will be taken for Full Blood Count (FBC) with Differential and Coagulation parameters (PT, aPTT, INR).
- Physical examination as per the institution's normal procedure.
- Changes in concomitant medications.
- Date of hospital discharge (for overall Length of Stay).
- Adverse events, including any complications potentially related to bleeding and/or thrombotic events.

7.1.5 30-day Follow-Up Visit (+/- 14 days)

The following information will be recorded either at the clinical follow-up visit approximately 30 days following surgery:

- Changes in concomitant medications, including use of any blood products following hospital discharge.
- Physical examination as per the institution's normal procedure.
- Adverse events, including any complications potentially related to bleeding and/or thrombotic events.

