7.3 Premature Withdrawal of Subjects for the Study

All randomised subjects should be encouraged to remain in the study until they have completed the 30-day follow-up visit. Subjects and/or their parent/legal guardian may discontinue participation in the study at any time and for any reason. However, if the subject decides to discontinue participation in the study, the reason must be documented when possible. Reasons for early withdrawal include, but are not limited to:

- Consent withdrawn by the subject or parent/legal guardian;
- Subject refusal to complete study visits and/or procedures;
- Lost to follow-up: a recorded delivery letter will be sent to the subject at their last known address, after a minimum of three attempts to reach the subject by telephone have failed. If communication via certified letter is unsuccessful, the subject will be considered lost to follow-up;
- Adverse events.

Subjects who discontinue from the study prematurely will not be replaced.

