ETHICON will provide each site with computer-generated randomization envelopes, each bearing the subject randomization number, and containing the treatment allocation. Treatment, either EVARREST or SURGICEL, will be assigned randomly to each subject on a 1:1 basis. In the event that a potential subject fails intraoperative criteria (i.e. no TBS identified, or an intraoperative exclusion), and is not randomized to the study, the unused randomization envelope should be returned to the series, and used for the next subject. Given the difference between the two treatment groups, it will not be possible for the surgeon to be blinded to the treatment. However, to avoid any bias in the conduct of the surgical procedure, randomization should only take place after completion of the following steps:

1. EVARREST and SURGICEL will be prepared and available in the sterile field in the operating room, ready for administration for each patient.
2. The investigator must perform the surgical procedure according to his/her standard of care.
3. Once the investigator encounters an appropriate hepatic parenchyma or soft tissue TBS related to the primary operative procedure, randomization should immediately take place. The randomization envelope will be opened simultaneously with starting the stopwatch.

Subjects will be followed post-operatively through hospital discharge and at 30 days (± 14 days) post-surgery.

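### Protocol section 9.6 ends follow-up of serious and product-related adverse events at the last visit, even when they are still open

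*Protocol*

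**What the plan says.** Protocol section 9.6 sets one stopping rule for every adverse event: "All AEs will be followed until completion of the 30-day follow-up visit or until a stable resolution, whichever is sooner". The same section sets the period in which events are collected. It starts at randomisation and continues "throughout the hospital admission, and until completion of the 30-day follow-up visit". For each event, the AE form must carry onset and resolution dates, severity, action taken, outcome, relationship to the product and seriousness.

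The visit window is the same in both documents. The Protocol synopsis says "Subjects will be followed post-operatively through hospital discharge and at 30 days (+/-14 days) post-surgery", and SAP section 2 says "Subjects will be followed post-operatively through hospital discharge and at 30 days (± 14 days) post-surgery". Protocol section 7.3 treats that visit as the end of participation: "All randomised subjects should be encouraged to remain in the study until they have completed the 30-day follow-up visit". The Schedule of Events shows nothing after it.

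Protocol sections 9.2 to 9.3 define serious and unexpected events. Section 9.7 gives reporting times: 24 hours for the investigator to report an SAE, seven or fifteen calendar days for a suspected unexpected serious adverse reaction, and two weeks to enter other AEs in the database. None of these sections says how long a serious event is followed.

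**The concern.** Because the rule takes the earlier of two endpoints, the visit is a hard stop for any event that has not settled. For a minor event that is a reasonable economy. For a serious event, or one the investigator thinks the product may have caused, how the event ended is part of the safety information that the trial exists to provide. Safety is a joint objective with effectiveness, and bleeding-related and thrombotic events are named endpoints.

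The rule also fits poorly with the form it serves. Section 9.6 asks for a resolution date and an outcome for every event. For an event open at the visit, no resolution date exists and the outcome can only be a status on that day. SAP section 10.3.1 plans to derive AE duration for the adverse event listing, which needs an end date.

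The stopping point also varies between subjects because of scheduling, not because of the event.

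**Working it through.** The plan states no figure on this point, so there is none to reproduce. The check is a reading of the relevant sections plus simple arithmetic on the visit window.

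**Step 1: is there an exception elsewhere?**

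- Protocol 9.6: one rule for all AEs; neither seriousness nor relatedness changes it.
- Protocol 9.2 to 9.3: definitions only.
- Protocol 9.7: deadlines for reporting and database entry only.
- Protocol 7.1.5, 7.3 and Schedule of Events: the 30-day visit is the last scheduled contact.
- SAP 8.5.1: rules for incomplete dates, and no rule for an event with no end date because it is continuing.
- SAP 10.3.1: AE duration is a derived item in the adverse event listing.

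None of these extends follow-up of an open serious or product-related event.

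**Step 2: when does follow-up stop?** Inputs: nominal visit day 30 and window 14 days (Protocol synopsis and 7.1.5; SAP section 2).

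- Earliest permitted visit: 30 − 14 = day 16.
- Latest permitted visit: 30 + 14 = day 44.
- Spread between subjects: 44 − 16 = 28 days.

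For an event that starts on day t and is still open at a visit on day V, follow-up required by the protocol lasts V − t days, with V between 16 and 44. An event that starts on the day of surgery (t = 0) is followed for at least 16 and at most 44 days. Two identical open events with the same onset day can differ by up to 28 days in required follow-up, depending only on when the visit was booked.

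**Step 3: what is lost and what is kept?**

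- Kept: the event itself, its coding, seriousness and relatedness, the 24-hour report if it is serious, and its status at the visit. Outcome is a field on the AE form, and nothing prevents entry of a status such as ongoing.
- Not required: the final outcome, the resolution date and hence the duration.

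**Step 4: which planned outputs depend on what is lost?** The AE endpoints in SAP sections 3 and 9.1 are incidences or proportions of subjects. The AE tables in SAP section 10.2.2 are organised by category, MedDRA term, seriousness and relatedness. Judged by their titles and notes (the table shells were not available), none tabulates final outcome or duration. The effect is confined to the listings and to the clinical account of individual events.

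**The case against.** The best defence is that nothing the plan analyses depends on the missing information. An open SAE is still reported, counted, coded and shown with its last known status. That stands, and it is why the point is of low severity. A reader might infer that the outcome of such an event is wholly unknown, or that the safety counts are biased. The documents support neither reading: only the course after the visit is missing.

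A second defence is that other material may already require longer follow-up. The Investigator's Brochure and the SAE form instructions were not available, and Protocol section 10.4.2 commits the trial to Good Clinical Practice and to national and regional requirements. This limits the point to the protocol text. It does not remove it, because sections 9.6 and 9.7 do not refer to those sources for a longer rule and section 9.6 as written sets a shorter one.

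Two stronger readings are tempting and should not be adopted:

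- *Absorption.* Protocol section 1 says "product is absorbed by the body, which is expected to occur within approximately 8 weeks". Eight weeks is 8 × 7 = 56 days, which is 56 − 44 = 12 to 56 − 16 = 40 days after the visit. A reader might infer that follow-up of open events is too short by that amount. But the figure is an approximate upper bound from rodent and swine models. The gap also concerns detection of new events after the visit, which is a separate matter that the fix below does not address.
- *Share of the arm.* With at least 40 subjects randomised 1:1, an arm has about 40 / 2 = 20, and one event is 1/20 = 5%. A reader might take this as the size of the problem. It is only the weight of one subject; the documents give no basis for expecting one such event, or any.

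Finally, day 16 is the earliest permitted visit, not the expected one.

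**Conclusion.** The point holds in a narrow form. Under Protocol section 9.6 as written, follow-up of an SAE or product-related AE that is still open ends at the last visit, somewhere between day 16 and day 44, and no other section of the Protocol or SAP overrides this. The final outcome, resolution date and duration of such an event need not be obtained.

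Severity is low. The primary endpoint and the planned AE incidence tables do not change. How often the rule would bite cannot be estimated, because neither document gives AE rates or durations for this trial. The conclusion assumes that no document outside the Protocol and SAP sets a longer rule. The term for settled events in section 9.6 is also undefined, so sites may differ on when an event counts as closed.

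**What to change.** In Protocol section 9.6, keep the present stopping rule for other AEs. Add that SAEs, and AEs rated Possible or Related to the investigational product (the categories already in section 9.4), are followed for outcome after the 30-day visit until resolution or a stable state, or until a stated data cut-off. The final outcome and its date are then recorded. Say in a few words what counts as a stable state.

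In the SAP, add a line on how an event still open at the cut-off is shown in the listing and how its duration is handled.

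This is a cheap improvement. It adds no scheduled visit and changes neither treatment nor the primary endpoint. The cost is a few extra site contacts for subjects with open serious or related events. Database lock may also have to wait a short time for the last of them, unless a cut-off is set.

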9.7 Adverse Event Reporting

It is a requirement that the Investigator promptly reports all SAEs (irrespective of relationship) as soon as possible, but no later than 24 hours after becoming aware of the event occurring.

Suspected, unexpected serious adverse drug reactions (SUSARs) will be reported to all relevant competent authorities, and IRBs /Ethics Committees within the required timeframes of seven calendar days for SUSARs that are fatal or life-threatening, and fifteen calendar days for all other SUSARs.

All other Adverse Events (AEs) must be reported (entered) into the [REDACTED] clinical trial database (electronic case report form (eCRF) within two weeks from the date the site becomes aware of the AE.

10 REGULATORY OBLIGATIONS

10.1 Informed Consent

Prior to participation, the study procedures and any known or likely risks will be explained to the subjects and/or their parent/legal guardian by the investigator or other medically qualified co-investigator. An Informed Consent Form will also be provided containing all the required information. Any questions will be answered and the patient and/or their parent/legal guardian will then be given sufficient time to consider their participation in the study before signing a consent form. Subjects and/or their parent/legal guardian should receive a copy of the Informed Consent Form. In addition, assent must be obtained from paediatric subjects who possess the intellectual and emotional ability to comprehend the concepts involved in the trial. If the paediatric subject is not able to provide assent (due to age, maturity and/or inability to intellectually and/or emotionally comprehend the trial), the parent/legal guardian's written Informed Consent for the subject will be acceptable for the subject to be included in the study.

The Investigator (or designee) will explain that the subjects and their parent/legal guardian are completely free to refuse to enter the study or to withdraw from it at any time, without any consequences for their further care and without the need to justify.

Each subject and/or their parent/legal guardian will be informed that the subject's source medical records may be checked by representatives from the Sponsor or from a regulatory agency, in accordance with applicable regulations. However, they should be made aware that all information will be treated with confidentiality, and a study ID code or number will identify them.

10.2 Institution Approval / Ethics Committees

The investigator must submit the Protocol and the Consent/Accent Form to the appropriate Institution department/EC according to local requirements. Approval from the Institution/EC must be obtained prior to starting any study-related procedure.

